11. ANNEXES

11.1. Business rules for standard data derivations and statistical methods

This section contains GSK Vaccines' standard rules for data display and derivation for clinical and epidemiological studies. These rules will be applied along with those detailed in section 10 (additional study-specific rules)

11.1.1. Handling of missing data

11.1.1.1. Dates

When partially completed dates (i.e. with missing day or month) are used in calculations, the following standard rules will be applied:

- A missing day will be replaced by 15
- A missing day and month will be replaced by June 30th.

The following exceptions apply:

- Adverse event start dates with missing day:
 - If the event starts in the same month as at least one of the study doses, the contents of AE.AESTRTPT (the flag indicating if the event occurred before or after vaccination) will be used to complete the date. If 'after vaccination' is selected, the imputed start date will match the first (or only) study dose given during that month. If 'before vaccination' is selected, the imputed date will be one day before the first (or only) study dose given during that month.
- Adverse event start dates with missing day and month:
 - If the event starts in the same year as at least one of the study doses, the contents of AE.AESTRTPT (the flag indicating if the event occurred before or after vaccination) will be used to complete the date. If 'after vaccination' is selected, the imputed start date will match the first (or only) study dose given during that year. If 'before vaccination' is selected, the imputed date will be one day before the first (or only) study dose given during that year.

All other cases of incomplete AE or concomitant medication/vaccination start date will follow the standard rules above.

11.1.1.2. Laboratory data

Missing laboratory results (including immunological data) will not be replaced.

11.1.1.3. Daily recording of solicited symptoms

11.1.1.3.1. Studies with electronic diaries

For studies using electronic diaries for the collection of solicited symptoms, symptoms will be considered present only when a daily recording of grade 1 or more is present.

11.1.1.3.2. Studies with paper diaries

For studies using paper diaries which have questions in the CRF indicating the presence or absence of solicited symptoms, the following rules are applicable.

Denominators for the summary of local (or general) solicited symptoms will be calculated using the number of subjects who respond "Yes" or "No" to the question concerning the occurrence of local (or general) symptoms.

When a specific symptom is marked as having not occurred following a specific vaccination (i.e. SDTM CE.CEOCCUR=N for the specified post-vaccination period for the symptom in question), all daily measurements will be imputed as Grade 0.

When a specific symptom is marked as having occurred following a specific vaccination (i.e. SDTM CE.CEOCCUR=Y for the specified post-vaccination period for the symptom in question), any missing daily recordings will be given imputed values to allow them to contribute to the 'Any' rows but not to specific grade rows of the symptom summary tables.

When the occurrence of a specific symptom is not present (i.e. SDTM CE.CEOCCUR is neither Y nor N for the specified post-vaccination period for the symptom in question) but the group of symptoms (local or general) is marked as having occurred (i.e. SDTM CE.CEOCCUR=Y), all missing daily recordings will be given imputed values to allow them to contribute to the 'Any' rows but not to specific grade rows of the symptom summary tables.

The following table shows how subjects contribute to each category for a specific solicited symptom over the Day X to Day Y post-vaccination period:

Solicited symptom category	Subjects included in the calculation of the numerator
Any	All subjects with at least one occurrence of the symptom at grade 1, grade 2, or grade 3 between Day X and Day Y or with the symptom marked as present and at least one missing daily recording between Day X and Day Y
At least grade 1	All subjects with at least one occurrence of the symptom at grade 1, grade 2, or grade 3 between Day X and Day Y
At least grade 2	All subjects with at least one occurrence of the symptom at grade 2 or grade 3 between Day X and Day Y
At least grade 3	All subjects with at least one occurrence of the symptom at grade 3 between Day X and Day Y

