All cases of severe malaria and cerebral malaria will be reported as SAEs and clinical details of each case will be reported in a specific eCRF screen (refer to Section 9.1.5).

9.1.3. **Solicited adverse events**

9.1.3.1. **Solicited local (injection-site) adverse events**

The following local (injection-site) AEs will be solicited:

Table 24 Solicited local adverse events

All age groups
Pain at injection site
Redness* at injection site
Swelling at injection site

* In case the principal investigator or designate is unable to determine the extent of redness on darkly pigmented skin, it will be reported as uninterpretable in the eCRF

9.1.3.2. **Solicited general adverse events**

The following general AEs will be solicited:

Table 25 Solicited general adverse events

Infant/Toddler/Child (< 6 years)
Drowsiness
Fever
Irritability/Fussiness
Loss of appetite

Note: Temperature will be recorded daily. Should additional temperature measurements be performed at other times of day, the highest temperature will be recorded in the eCRF.

9.1.4. Clinical laboratory parameters and other abnormal assessments qualifying as adverse events or serious adverse events

In absence of diagnosis, abnormal laboratory findings (e.g. clinical chemistry, hematology, urinalysis) or other abnormal assessments (e.g. failure to thrive) that are judged by the investigator to be clinically significant will be recorded as AE or SAE if they meet the definition of an AE or SAE (refer to Sections 9.1.1 and 9.1.2). Clinically significant abnormal laboratory findings or other abnormal assessments that are present at baseline and significantly worsen following the start of the study will also be reported as AEs or SAEs.

The investigator will exercise his or her medical and scientific judgement in deciding whether an abnormal laboratory finding or other abnormal assessment is clinically significant.

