11.6. Derived and transformed data

• Immunogenicity

- A subject seropositive for anti-CS antibody will be a subject whose antibody concentration will be greater than or equal to the cut-off value (anti-CS ≥ 0.5 EU/ml).
- Seroprotection rate for anti-HBs antibody is defined as the percentage of subjects with antibody concentration greater than or equal to an established cut-off (anti-HBs ≥ 10 mIU/ml).
- The geometric mean concentration (GMC) calculations will be performed by taking the anti-log of the mean of the log transformations (base 10). Antibody concentrations below the cut-off of the assay will be given an arbitrary value of half the cut-off for the purpose of GMC calculation.

- Handling of missing data: For a given subject and a given immunogenicity measurement, missing or non-evaluable measurements will not be replaced. Therefore, an analysis will exclude subjects with missing or non-evaluable measurements.
- **Reactogenicity and safety**
 - Handling of missing data: subjects who missed reporting symptoms (solicited/unsolicited or concomitant medications) will be treated as subjects without symptoms (solicited/unsolicited or concomitant medications, respectively). In case of significant non-compliance of study procedures for reporting symptoms, the analysis plan will be reassessed to ensure more accurate reporting of study data by further analysis.
 - For the analysis of solicited symptom, missing or non-evaluable measurements will not be replaced. Therefore the analysis of the solicited symptoms based on the TVC will include only subjects/doses with documented safety data (i.e. symptom screen/sheet completed).

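### The SAP counts a solicited symptom with no recorded Yes or No as present in the 'Any' row, against the protocol and its own numerator table; uninterpretable redness is where this could matter

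*SAP*

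**What the plan says.** SAP 11.1.1.3.2 applies to trials of this kind: "For studies using paper diaries which have questions in the CRF indicating the presence or absence of solicited symptoms". One of its rules has two triggers. The first is that "CE.CEOCCUR is neither Y nor N for the specified post-vaccination period for the symptom in question". The second follows directly: "but the group of symptoms (local or general) is marked as having occurred". When both hold, "all missing daily recordings will be given imputed values to allow them to contribute to the 'Any' rows but not to specific grade rows".

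The table that closes the section defines who enters the 'Any' numerator. It admits a child with a graded occurrence, or one "with the symptom marked as present and at least one missing daily recording between Day X and Day Y". The denominator is the number of children with a Yes or No to the group-level question (local or general), not to the individual symptom.

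Protocol 11.6 states: "For the analysis of solicited symptom, missing or non-evaluable measurements will not be replaced". It goes on to restrict the analysis to subjects and doses with a completed symptom sheet.

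The footnote to Table 24 (Protocol 9.1.3.1), repeated under Table 28, covers redness whose extent cannot be determined on darkly pigmented skin: "it will be reported as uninterpretable in the eCRF". The SAP does not mention this category. SAP section 10, which lists changes from the planned analyses, does not mention the blank-flag rule.

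**The concern.** A symptom that nobody recorded as present or absent should not become a positive finding. The blank-flag rule makes it one, on the strength of a different symptom in the same group.

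Redness is the symptom for which the protocol itself foresees a non-evaluable entry. Its purpose for collecting reactogenicity data (Protocol section 3, safety monitoring) is to characterise fractional doses relative to full doses. If uninterpretable redness reaches the database as a blank flag, part of the rate of pain and swelling is carried into the redness row. Where that rate differs between full and fractional doses, so may the carried-over part. With 50 children per group in the reactogenicity sub-cohort, a few children move a row visibly. In addition, two programmers working from the same section, one from the text and one from the table, could produce different redness rates.

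**Working it through.** The documents give no rate for redness, for uninterpretable redness or for other local symptoms, so there is no stated figure to reproduce. The check has two parts.

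**1. How each possible coding of uninterpretable redness would be handled**

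| Redness flag | Local group | SAP text | SAP numerator table |
|---|---|---|---|
| Yes, size missing | Yes | in 'Any' | in 'Any' |
| Blank | Yes | in 'Any' | not in 'Any', kept in denominator |
| Blank | No | not in 'Any', kept in denominator | same |
| No | either | Grade 0 on all days | same |

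Text and table disagree only in the second row. The last three rows all keep a child whose redness could not be assessed in the denominator, as a case or as a non-case.

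**2. Size if the entry is stored as a blank flag**

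Notation, all values assumed:
- u: share of children with uninterpretable redness, taken as equal in both arms and independent of r and p
- r: redness rate among children in whom it can be assessed
- p: share with another local symptom (pain or swelling), which sets the local group to Yes

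Rate in the 'Any' redness row:
- SAP text rule: (1 − u)r + up
- SAP numerator table read literally: (1 − u)r
- Unassessable redness excluded: r

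Excess of the text rule over exclusion, per arm: (1 − u)r + up − r = u(p − r).

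Effect on the full-minus-fractional difference: u[(p_full − p_fx) − (r_full − r_fx)].

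With r = 5% in both arms and p = 40% (full) and 20% (fractional):
- u = 5%: full 0.95 × 5 + 0.05 × 40 = 6.75%; fractional 0.95 × 5 + 0.05 × 20 = 5.75%. False difference 1 point.
- u = 20%: full 0.80 × 5 + 0.20 × 40 = 12.0%; fractional 0.80 × 5 + 0.20 × 20 = 8.0%. False difference 4 points, or 6 against 4 children per 50.

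Under exclusion, or under the table read literally, the difference in this example is 0.

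The effect is not always positive:
- r = 5%/5%, p = 10%/10%: the contrast effect is 0 at every u.
- r = 10%/2%, p = 10%/10%, u = 20%: 0.20 × (0 − 8) = −1.6 points, so a true 8-point difference is shown as 6.4.

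For scale, the exact 95% confidence interval is 0.5% to 13.7% for 2/50 and 2.2% to 19.2% for 4/50. A shift of 1 to 4 points is small beside the sampling error of one group.

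**The case against.** The strongest reply is that the link from the uninterpretable entry to a blank occurrence flag is nowhere in the documents. The protocol footnote concerns the extent of redness, and Table 28 records redness as a diameter. The entry may therefore mean that redness was seen but could not be measured, with the flag at Yes. Counting that child under 'Any' and in no grade row would then be sensible. The CRF questions are not shown, and the rule belongs to a standard annex that was not written for this trial. All of this stands. It means that the effect on redness is conditional. It does not remove the conflict between the text rule, the numerator table and Protocol 11.6, which holds for any blank flag.

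A second reply is that Protocol 11.6 works at the level of subjects and doses with a completed sheet, and that its preceding bullet treats missed reporting as no symptom. This also stands in part: the protocol forbids replacement but does not prescribe a redness-specific denominator. Leaving unassessable redness out of the denominator is an analytical choice consistent with 11.6, not a quotation of it. Neither protocol rule, however, turns an unassessed symptom into a positive one.

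A third reply is that little depends on it. The tables give within-group percentages with exact intervals and no planned between-group test. The graded rows do not change, and comparing 'Any' with 'at least grade 1' would expose an excess. The row for at least one local event does not change either, since the child already has another local symptom. This is correct, and it limits the severity.

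**Conclusion.** The contradiction is real and undeclared: the SAP text imputes presence for a blank flag, while Protocol 11.6 and the SAP's own numerator table do not. The consequence for redness depends on how the uninterpretable entry is coded, and on u, p and r, none of which the documents give. On the assumed values above the false full-versus-fractional difference is 1 to 4 points for u between 5% and 20%; on other values it is zero or negative.

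A reader might infer more: that the plan definitely counts uninterpretable redness as redness, that it does so in proportion to pain, and that the comparison of doses is therefore distorted. The documents do not support this. The coding is not stated, the trigger is any other local symptom and not pain alone, the excess against exclusion is u(p − r), and the direction of the contrast effect cannot be fixed. Only the descriptive 'Any' row for the individual symptom is affected, and no efficacy or primary conclusion is touched. Severity is low to moderate.

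**What to change.** In SAP 11.1.1.3.2, delete the sentence that imputes a blank-flag symptom into the 'Any' row, so that the text agrees with the numerator table and with Protocol 11.6. Then add how uninterpretable redness is coded in the eCRF and the analysis data, with two rules:

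- Where the presence of redness could not be assessed, leave that child out of both numerator and denominator of the redness row for that dose, and show the number uninterpretable by group and dose.
- Where redness was marked present and only its size could not be measured, keep the child in 'Any' and out of the grade rows.

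Deleting the imputation alone is not enough, because the group-level denominator would still count unassessable children as free of redness and give (1 − u)r instead of r. If the sponsor prefers to keep the blank-flag rule, it should be listed in SAP section 10 with a reason, and the numerator table should be changed to match.

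The cost is a few sentences and one extra column. The redness denominator shrinks by u × 50 per group: 2 or 3 children at u = 5%, and 10 at u = 20%. The reported counts let the reader judge whether the remaining children are enough.

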11.1.1.4. Unsolicited adverse events

Missing severity, relationship with study vaccine, and outcome of unsolicited adverse events will not be replaced and will appear as 'UNKNOWN' in all statistical output.

11.1.2. Data derivation

11.1.2.1. Age at vaccination in days

When age at vaccination is to be displayed in days, it will be calculated as:

Age = date of vaccination minus date of birth

11.1.2.2. Age at vaccination in months

When age at vaccination is to be displayed in months, it will be calculated as the number of complete calendar months between the date of birth (DOB) and the date of vaccination. For example:

DOB = 10JUN2017, Date of vaccination = 09JUL2018 -> Age = 12 months

DOB = 10JUN2017, Date of vaccination = 10JUL2018 -> Age = 13 months

11.1.2.3. Age at vaccination in years

When age at vaccination is to be displayed in years, it will be calculated as the number of complete calendar years between the date of birth and the date of vaccination. For example:

DOB = 10SEP1983, Date of vaccination = 09SEP2018 -> Age = 34 years

DOB = 10SEP1983, Date of vaccination = 10SEP2018 -> Age = 35 years

11.1.2.4. Weight

Weight will be presented in kilograms. Weights reported in pounds will be converted as follows:

Weight in kilograms = Weight in pounds / 2.2

11.1.2.5. Height

Height will be presented in centimeters. Heights reported in feet and inches will be converted as follows:

Height in centimeters = Height in inches $\times 2.54$

11.1.2.6. Body mass index (BMI)

BMI will be calculated as follows:

 $BMI = (Weight in kilograms) / (Height in meters)^2$

11.1.2.7. Temperature

Temperatures will be presented in degrees Celsius (°C). Temperatures reported in degrees Fahrenheit (°F) will be converted as follows:

Temperature (Celsius) = $((Temperature (Fahrenheit) - 32) \times 5)/9$

11.1.2.8. Numerical serology results

Numerical serology results will be derived from the content of IS.ISORRES in the SDTM dataset. For assays with a specific cut-off, the following derivation rules apply:

IS.ISORRES	Derived value
"NEG", "-", or "(-)"	cut-off/2
"POS", "+", or "(+)"	cut-off
"< value" and value is <= assay cut-off	cut-off/2
"< value" and value is > assay cut-off	value
"> value" and value is < assay cut-off	cut-off/2
"> value" and value is >= assay cut-off	value
"value" and value is < cut-off	cut-off/2
"value" and value is >= cut-off	value
All other cases	missing

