APPENDIX A LABORATORY ASSAYS

Anti-CS antibody

Antibody concentrations against *P. falciparum* CS-repeat region will be measured at CEVAC by a standard ELISA methodology using plate adsorbed recombinant R32LR antigen, as described by Clement *et al.* [Clement, 2012]. Anti-CS antibody concentrations will be determined relative to a standard reference antibody as a control according to standard operating procedures from the laboratory. The cut-off for the assay is 0.5 EU/ml. Results will be reported in EU/ml.

Anti-HBs antibody

Anti-HBs antibody concentrations will be determined using commercially available CLIA kits ADVIA® Centaur anti-HBs2 manufactured by Siemens Healthcare. The cut-off for the assay is 6.2 mIU/ml. Results will be reported in mIU/ml.

Anti-CS avidity

For the measurement of avidity of IgG against *P. falciparum* CS-repeat region, samples will be evaluated as described by Clement *et al.* [Clement, 2012], but in two different plates; one treated with a chaotropic agent and one untreated plate. As chaotropic agent a 1 M solution of ammonium thiocyanate (NH₄SCN) is added in the treatment plate while 0.05% Tween-20 in phosphate buffered saline (PBS) is added in the untreated plate and both CS ELISA plates are further washed and developed as described [Clement, 2012]. The avidity index (AI) is calculated as the ratio of the concentration of anti-CS IgG (EU/ml) that remained bound to the coated antigen after treatment with NH₄SCN, divided by the concentration of IgG (EU/ml) that remained bound to the coated antigen in the untreated plate.

Blood smear and filter paper for assessment of *P. falciparum* parasitemia

Blood slide preparation and slide reading will be performed according to standard operating procedure from the Malaria Diagnostics Centre of Excellence, Kisumu, Kenya.

Blood drops will be collected on a filter paper for the ancillary study that will evaluate the incidence of *P. falciparum* infection assessed by PCR and parasite genotyping.

Hemoglobin, WBC, platelets, ALT and creatinine

The measure of hematology and biochemistry parameters will be done at each study center using validated automated analyzers and according to the equipment specifications.

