7.4. Immunogenicity

7.4.1. Analysis of immunogenicity planned in the protocol

The primary analysis of immunogenicity will be based on the PPS for immunogenicity; however, analyses on the ES will also be performed.

In the immunogenicity subset (first 50 subjects enrolled in each group), the percentage of subjects with seropositive levels of anti-CS (proportion of subjects with anti-CS antibody concentrations greater than or equal to 1.9 EU/ml) with 95% CI will be determined at specified blood sampling timepoints in each group (see Section 2 – Sampling schedule). Anti-CS antibody concentrations will be summarized by geometric mean concentrations (GMCs) with 95% CI. Anti-CS antibody concentrations one month after the third dose and each subsequent dose of study vaccine will also be investigated using reverse cumulative distribution (RCD) curves.

The seroprotective level for anti-HBs is ≥ 10 mIU/ml. In the immunogenicity subset, the percentage of subjects with protective levels of anti-HBs (≥ 10 mIU/ml) with 95% CI will be determined at specified blood sampling timepoints in each group (see Section 2 – Sampling schedule). Anti-HBs antibody concentrations will be summarized by GMCs with 95% CI. Anti-HBs antibody concentrations one month after the third dose and each subsequent dose of study vaccine will also be investigated using RCD curves.

For the analysis of the tertiary objective, avidity/affinity index and avidity maturation will be summarized by mean, SD, median and quartile.

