10. CHANGES FROM PLANNED ANALYSES

The Total Vaccinated Cohort and the According To Protocol cohort have been renamed Exposed Set (ES) and Per-Protocol Set (PPS) respectively.

The seropositivity threshold for anti-CS has been updated from 0.5 EU/ml to 1.9 EU/ml.

A Solicited Safety Set has been added in the analysis set section to fit with the new statistical rules and layouts applicable from the 12th of November 2018.

For purposes of analyses and to simplify the naming convention of the groups in Figure 1 haven been simplified. The label names of the study groups have been renamed according to the following table:

Vaccination schedule	Group label in protocol	Group label in SAP
RTS,S/AS01 _E full dose given at Month 0, Month 1, Month 2 and a fourth dose at Month 20	R012-20	R012-20
RTS,S/AS01 _E full dose at Month 0, Month 1, Month 2, an early fourth dose at Month 14 and yearly full doses at Month 26 and Month 38	R012-14-mD	R012-14
RTS,S/AS01 _E full dose at Month 0 and Month 1, RTS,S/AS01 _E fractional dose (1/5 th dose) at Month 2 and yearly fractional doses at Month 14, Month 26, Month 38	Fx012-14-mFxD	Fx012-14
RTS,S/AS01 _E full dose at Month 0 and Month 1, RTS,S/AS01 _E delayed fractional third dose (1/5 th dose) at Month 7 and yearly fractional doses at Month 20 and Month 32	Fx017-mFxD	Fx017-20
Rabies vaccine at Month 0, Month 1 and Month 2	Control	Control

A sequential approach to the analysis of incremental efficacy over the 12-month period post-dose 3 of a schedule with a fractional dose at month 7 versus 3 full doses was implemented (see section 8).

204889 (Malaria-094) Statistical Analysis Plan

The following analyses were added or modified:

- Unsolicited adverse events within 7 days after each vaccination will be described in addition to the 30 days analysis
 - Analyses on the occurrence of PIMDs (described in section Secondary endpoints) were added in section Analysis of safety and reactogenicity planned in the protocol, as they were missing in the protocol
- Secondary endpoint for efficacy
 - Analyses considering different calendar follow-up time was updated. In the protocol an indirect comparison was suggested taking into account incidence in controls, while for the SAP another proposal is suggested as described in section 7.3.1.1
 - Analysis of incident infection will only be performed up to M20 since infection with *P. falciparum* was regularly (monthly) evaluated until this time point.

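### The SAP serology table turns an anti-HBs result reported as below 10 mIU/ml into 10, which counts as seroprotected; other one-sided results can be given a class the report leaves open

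*SAP*

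**What the plan says.** SAP 11.1.2.8 introduces its table with "For assays with a specific cut-off, the following derivation rules apply". Two rows matter here:

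- "< value' and value is > assay cut-off": the derived value is the reported value.
- "> value' and value is < assay cut-off": the derived value is half the cut-off.

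Only results that fit none of the listed patterns become missing.

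The cut-offs and thresholds are these:

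- **Anti-HBs.** Protocol Appendix A: "The cut-off for the assay is 6.2 mIU/ml". SAP 7.4.1: "The seroprotective level for anti-HBs is ≥ 10 mIU/ml".
- **Anti-CS.** Protocol Appendix A: "The cut-off for the assay is 0.5 EU/ml". SAP section 10: "The seropositivity threshold for anti-CS has been updated from 0.5 EU/ml to 1.9 EU/ml". SAP section 10 speaks of the seropositivity threshold. It does not say whether the assay cut-off used in the derivation table moves with it. SAP 11.1.2.9 says only that the laboratory fixes the cut-off before the analysis.

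Protocol 11.6 gives half the cut-off to concentrations below the assay cut-off and adds that "missing or non-evaluable measurements will not be replaced".

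**The concern.** A result reported as `<v` is known only to lie below v. Setting it to v puts it at a value the report rules out. If v equals the threshold for a class defined as at or above that threshold, the sample enters the class it was reported not to belong to. In the other direction, a result known only to exceed a low value is set to half the cut-off and called negative, although it may be positive.

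The derived numbers feed anti-CS seropositivity, anti-HBs seropositivity and seroprotection, the GMCs and the reverse cumulative curves. All of these come from 50 children per group, so a single sample is visible in a reported percentage.

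**Working it through.** **Inputs.** Assay cut-off c: 6.2 (anti-HBs) and 0.5 (anti-CS) from Protocol Appendix A, or 1.9 for anti-CS if the SAP change also applies to the table. Threshold t: 10 for anti-HBs seroprotection and 1.9 for anti-CS seropositivity (SAP 7.4.1). For anti-HBs seropositivity I take t = 6.2, the assay cut-off, because the SAP states no separate figure. Group size is 50. The frequency of one-sided results is not given, so 1 and 5 of 50 are shown as assumptions.

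**The plan's own figure.** No stated figure depends on these rows. The only immunogenicity figure given, in Protocol 11.4 (GMC 50, log SD 0.5, n = 50), reproduces: 50 × 10^(±1.96 × 0.5/√50) = 36.3 to 68.8.

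**Row for `<v` with v > c.** The derived value is v, so the sample is classed positive when v ≥ t. The report rules out positive when v ≤ t. Both hold only when v = t, and since v > c this requires t > c.

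- Anti-HBs seroprotection: t = 10 > c = 6.2, so `<10` is contradicted.
- Anti-CS with c = 0.5: t = 1.9 > c, so `<1.9` is contradicted.
- Anti-CS with c = 1.9, and anti-HBs seropositivity: t = c, so no contradiction is possible. Every such result is classed positive while the report allows either class.

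**Row for `>v` with v < c.** The derived value c/2 is always below t, so the class is always negative. The report allows values on both sides of t. The class is therefore never contradicted and always open.

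| Assay (c; t) | Reported | Derived | Class given | Class the report allows |
|---|---|---|---|---|
| anti-HBs (6.2; 10) | `<8` | 8 | below | below |
| anti-HBs (6.2; 10) | `<10` | 10 | seroprotected | below only |
| anti-HBs (6.2; 10) | `<12` | 12 | seroprotected | either |
| anti-HBs (6.2; 6.2) | `<8` | 8 | positive | either |
| anti-HBs (6.2; 6.2) | `>5` | 3.1 | negative | either |
| anti-CS (0.5; 1.9) | `<1.9` | 1.9 | positive | negative only |
| anti-CS (1.9; 1.9) | `<1.9` | 0.95 | negative | negative |
| anti-CS (1.9; 1.9) | `<3` | 3 | positive | either |
| anti-CS (1.9; 1.9) | `>1.5` | 0.95 | negative | either |

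**Derived number.** Under the first row it is always outside the reported range, because v is not less than v. Under the second it is outside whenever v ≥ c/2; for anti-HBs, `>5` becomes 3.1.

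**Size in a group of 50.**

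- Rates: 1/50 = 2 percentage points per reclassified sample. Clopper-Pearson 95% intervals: 0/50 = 0% (0 to 7.1); 1/50 = 2% (0.1 to 10.6); 5/50 = 10% (3.3 to 21.8).
- GMC, anti-HBs `<10` coded 10 rather than 3.1: (10/3.1)^(1/50) = 1.024 for one sample, and (10/3.1)^(5/50) = 1.124 for five.
- GMC, anti-CS `<1.9` coded 1.9 rather than 0.25 (c = 0.5): (1.9/0.25)^(1/50) = 1.041 for one sample, and 1.225 for five.

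**The case against.** The strongest reply is that the rows may never be used. SAP 11.1 presents the annex as the sponsor's standard rules for its studies, and the table also covers qualitative positive and negative reports. Both assays here are quantitative, and an ordinary below-cut-off result falls under an undisputed row that gives half the cut-off. Nothing says that either laboratory reports `<10` against a cut-off of 6.2. This stands: the effect on the trial's results cannot be established. It does not make the row right.

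Three stronger readings are tempting, and the documents do not support them.

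- **That the `>v` row calls samples seronegative against the report.** As shown above, it never contradicts the reported class. Not counting a sample as positive until it is shown to reach the cut-off is a defensible, conservative convention.
- **That baseline and Control samples are the most exposed because their values are low.** This is plausible for anti-CS. For anti-HBs, the one unconditional contradiction, Protocol 5.2 requires three documented doses of a hepatitis B-containing vaccine before entry, so low values cannot be assumed.
- **That the rows breach Protocol 11.6.** That section does not replace non-evaluable results, but it does not say that a one-sided result is non-evaluable. It lends support to the fix without proving a conflict.

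Simply setting such results to missing would also be a poor remedy for the GMC: it removes results known to lie below a bound and could push the mean upward.

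**Conclusion.** The rule is wrong as written, with a small effect. Anti-HBs `<10` is classed seroprotected against the report; neither SAP 11.1.2.9 nor the missing-data rule in SAP 11.1.1.2 repairs this. Anti-CS `<1.9` is classed seropositive against the report only if the table's cut-off is 0.5 EU/ml while the threshold is 1.9, which the SAP leaves unsettled. In the remaining problem cases the class is unsupported, not contradicted.

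The size rests on an unknown frequency. Immunogenicity objectives are descriptive, and SAP section 8 keeps these endpoints out of the testing hierarchy. The primary efficacy analysis and the safety analyses are untouched.

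**What to change.** Amend SAP 11.1.2.8 as follows:

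1. Classify one-sided results from the reported bound. `<v` with v at or below the threshold is below the threshold, so anti-HBs `<10` is not seroprotected.
2. Where the bound leaves the class open, treat the sample as non-evaluable for that classification only, and list it.
3. Keep these samples in the GMC, and show a sensitivity analysis with `<v` set to v and then to half the cut-off.
4. State whether the anti-CS assay cut-off used in the table is 0.5 or 1.9 EU/ml.

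The cost is a few rows of a derivation table, possibly a few samples non-evaluable for a rate, and one small sensitivity analysis. If no such results occur, nothing in the report changes.
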